# 4.5 Multiplicity

There are no pre-specified test hypotheses or assignments of statistical significance to study results requiring a consideration of adjustments for multiple testing.

# 4.6 Analysis Populations

The following analysis populations will be defined.

Enrolled Population: The enrolled population will include all subjects who signed the informed consent form and/or given assent.

Safety Population: The safety population will be defined as all subjects who received any amount of IP. All analyses will be based on the Safety Population, unless specified otherwise

For all efficacy analyses defined in this document, the Safety Population will be utilized.

Efficacy analyses combining HOPE-2-OLE data with either External Comparator for the PUL 2.0 Combined Total (ECP) or External Comparator for Cardiac (ECC) will use Safety Population for the HOPE-2-OLE subjects, and all subjects provided by ECP or ECC, unless specified otherwise

### 4.7 Subgroup Analyses

For select cardiac parameters, a subgroup analysis will be performed for subjects with >45% LVEF at baseline.

# **5 STUDY POPULATION PARAMETERS**

# 5.1 Eligibility and Informed Consent

Eligibility and informed consent parameters will be listed for the enrolled population and will include date of informed consent/assent, version of the HOPE-2-OLE protocol under which the subject was enrolled, and inclusion and/or exclusion criteria that were not met.

The number of subjects who met all screening eligibility criteria and reasons for screen failure will be summarized for the enrolled population.

# 5.2 **Protocol Deviations**

Protocol deviations will be listed for the safety population and may include, but not be limited to, the following categories:

- Visit not done or out-of-window
- Assessment not completed or out-of-window
- Inclusion/exclusion

- Informed consent/assent
- IP administration

The number and percentage of subjects with at least 1 protocol deviation and the number and percentage of subjects with at least 1 protocol deviation in a deviation category will be summarized. Likewise, the number and percentage of subjects with at least 1 major protocol deviations will be tabulated.

# 5.3 Demographics and Baseline Characteristics

Demographic and baseline characteristics will be listed and summarized for the safety population. Demographic characteristics will consist of sex, ethnicity, and race, as collected in the preceding HOPE-2 trial, and age in years at HOPE-2 OLE baseline.

Baseline characteristics will include ulna length, height, weight, body mass index (BMI), baseline PUL 2.0 entry item score, and baseline PUL 2.0 entry item score binary stratification (2, 3 vs 4, 5), where entry item score refers to the baseline OLE score, and length of Gap Phase in days.

Subject height will be calculated from the subject's ulna length: Height (cm) = [4.605 x Ulna Length (cm)] + [1.308 x Age (years)] + 28.003.

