## 4.8. Trial Population

The target population for this trial is pediatric and adult males with a diagnosis of DMD who participated in the HOPE-2 trial and completed the 12-month follow-up period and meet the OLE trial eligibility criteria (see Section 7) that focuses on minimizing the risks of participation in the extension trial.

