# 7.1. Subject Inclusion Criteria

Inclusion criteria will be assessed within 30 days prior to first infusion on Day 1 unless otherwise noted:

- 1. Documented enrollment in the HOPE-2 trial and completion of trial follow-up through Month 12
- 2. Willing and able to provide informed consent to participate in the trial if  $\geq 18$  years of age, and assent with parental or guardian informed consent if < 18 years of age
- 3. Adequate venous access for intravenous deramiocel infusions in the judgement of the Investigator
- 4. Assessed by the Investigator as willing and able to comply with the requirements of the trial

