#### Table 4:Height Calculation from Ulna Length

Height (cm) = [4.605 x Ulna Length (cm)] + [1.308 x Age (years)] + 28.003

Centimeter and year entries must include decimal places to the tenth place. If a subject is 18 years or older, enter "18" in the formula for age.

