# 7.2 Vital Signs, Height, Weight, and BMI

Vital signs will include systolic and diastolic blood pressures, pulse rate, respiratory rate, body temperature, and blood oxygen saturation (SpO2). Observed and change-from-baseline values will be summarized at each post-baseline visit. Baseline will be defined as the pre-infusion samples that are collected on Day 1. Scheduled assessments will be summarized, and unscheduled events will only be listed.

Listings of vital signs, ulna length, height, weight, and BMI will be provided. Height will be calculated from the subject's ulna length.

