# **8 DEVIATIONS FROM STATISTICAL METHODS IN THE PROTOCOL**

The statistical methods in this statistical analysis plan are consistent with those described in the Amendment 5 of the study protocol with the following exceptions:

- The wall thickness percentages for the cardiac MRI parameters (secondary efficacy) were not collected and thus not available for descriptive analysis.
- Cardiac MRI parameters were not collected at 12-months for the HOPE-2-OLE study.
- The secondary analyses (Distal level PUL 2.0 and Mid-level (elbow) PUL 2.0) which involved subgroup analyses based on the entry level item of PUL 2.0 at baseline will be reported without the subgroups due to the small sample size of the subgroups.

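### SAP 5.3 gives the ulna-based height formula without the protocol's rule to enter 18 as the age of adults, so height is overstated and BMI understated for any subject over 18 if programmed as written

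*SAP*

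**What the plan says.** SAP 5.3 (Demographics and Baseline Characteristics) lists height and BMI among the baseline characteristics and gives the derivation of height: "Height (cm) = [4.605 x Ulna Length (cm)] + [1.308 x Age (years)] + 28.003". It puts no condition on age. The only age variable the section names is "age in years at HOPE-2 OLE baseline".

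Protocol Table 4, under Section 10.1.2, has the same formula with two rules attached. On age it says "If a subject is 18 years or older, enter" 18 in the formula. On precision it says "Centimeter and year entries must include decimal places to the tenth place".

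SAP 7.2 promises further output: "Listings of vital signs, ulna length, height, weight, and BMI will be provided". It repeats that height comes from ulna length but adds neither rule. Footnote 7 of the SAP's schedule of assessments does not add them either.

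SAP Section 8 describes its methods as "consistent with those described in the Amendment 5 of the study protocol with the following exceptions". Three exceptions follow, and none concerns height.

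On who can enrol, Protocol 4.8 says "The target population for this trial is pediatric and adult males with a diagnosis of DMD". Inclusion criterion 2 in Protocol 7.1 has separate consent arrangements for subjects aged 18 or over and for those younger.

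**The concern.** The formula adds 1.308 cm of height for each year of age. The protocol stops that addition at 18; the SAP, as printed, lets it continue. The two documents therefore give different heights for the same ulna measurement in any subject over 18. The difference always runs the same way, with the SAP height taller and the BMI lower, so it does not average out across subjects.

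The baseline height and BMI summary and the height and BMI listings are exposed. Ulna length is scheduled at every visit and follow-up lasts about 60 months, so a subject who enters after his 13th birthday can pass 18 during the trial. Neither document says which age to use at later visits. If age at each visit is used, the discrepancy grows by 1.308 cm a year once a subject is past 18. If baseline age is used throughout, it stays constant.

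The PUL 2.0 and LVEF endpoints do not depend on height. SAP 6.4 applies the HOPE-2 body-surface-area calculation to the cardiac comparator in order to harmonize indexed volumes, but neither document gives that formula or its height source. An effect on the indexed volumes is therefore possible but not shown.

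**Working it through.** The documents give no worked height, so there is no stated figure to reproduce. The check compares the two printed rules.

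**Inputs from the documents**
- Coefficients 4.605 (ulna length), 1.308 (age) and 28.003 (constant), identical in SAP 5.3 and Protocol Table 4.
- Age entered as 18 at 18 or older: Protocol Table 4 only.
- Ulna length recorded to 0.1 cm: Protocol Table 4.
- 13 subjects in the open-label phase: SAP 4.1.

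**Assumed for illustration:** ages 20 and 23; Table 4 heights of 150, 160 and 170 cm; an ulna length of 25 cm; and the numbers of adults in the last step.

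**1. Height difference.** The SAP uses age and the protocol uses min(age, 18). The ulna term and constant cancel, leaving

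e = 1.308 x (age - 18) for age above 18, and zero otherwise.

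- Age 20: 1.308 x 2 = 2.62 cm.
- Age 23: 1.308 x 5 = 6.54 cm.

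Example with an ulna length of 25 cm at age 20:
- Protocol: 115.125 + 1.308 x 18 + 28.003 = 166.67 cm.
- SAP: 115.125 + 1.308 x 20 + 28.003 = 169.29 cm.
- Difference: 2.62 cm.

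**2. Comparison with the recording precision.** One 0.1 cm step of ulna length is worth 4.605 x 0.1 = 0.46 cm of height. The difference is 2.616 / 0.4605 = 5.7 steps at age 20 and 6.54 / 0.4605 = 14.2 steps at 23. This equals 0.57 and 1.42 cm of ulna length.

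**3. BMI.** Weight cancels, so the relative change is (H / (H + e))^2 - 1, where H is the Table 4 height.

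| Assumed Table 4 height | Age 20 | Age 23 |
|---|---|---|
| 150 cm | -3.40% | -8.18% |
| 160 cm | -3.19% | -7.70% |
| 170 cm | -3.01% | -7.27% |

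**4. Mean baseline height of 13 subjects.** With k adults of the same age, the shift is k x e / 13.
- No subject over 18: 0.
- One aged 20: 2.616 / 13 = 0.20 cm.
- Four aged 20: 4 x 2.616 / 13 = 0.80 cm.
- Four aged 23: 4 x 6.54 / 13 = 2.01 cm.

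**The case against.** The best defence is that the SAP only abbreviates. Table 4 is current protocol text, and Section 8 claims consistency with the protocol without listing height as an exception. On that reading the age rule still applies and nothing conflicts. Table 4 is also worded as a data-entry instruction and sits beside site measurement and training requirements. Height may therefore be calculated at the site or in the data capture system and simply carried into the analysis, in which case no error occurs. The number of subjects over 18 is unknown and could be zero at baseline.

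Part of this stands. The omission is certain; the resulting error is conditional on how height is programmed and on subjects' ages. But SAP 5.3 states that height will be calculated, prints a complete-looking formula and does not refer to Table 4. A programmer working from the SAP would enter actual age, because nothing there says otherwise. The general consistency statement does not supply the missing rule at the point of use.

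Two further objections are fair. Recording precision is not measurement or prediction error, so the multiples in step 2 show only that the difference exceeds rounding, not that it is clinically important. And Table 4 does not say which visit's age to use, so choosing age at the visit settles a point that both documents leave open.

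**Conclusion.** The concern holds, as a minor point. For any subject over 18, SAP 5.3 as printed gives a height that is 1.308 cm too large, by the protocol's own rule, for each year past 18. That size depends only on the two documents' formulas and not on ulna length. The BMI percentages depend on the assumed heights, and the shift in the group mean (0 to 2.0 cm in the scenarios shown) depends on assumed numbers and ages of adults. There is no discrepancy at 18.0 years or below, and none if Table 4 heights are used unchanged. The consequence is confined to descriptive height and BMI outputs; no efficacy result is shown to be affected.

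**What to change.** In SAP 5.3, and by reference in 7.2, replace the age term with min(age at the visit, 18), with age and ulna length to one decimal place as Table 4 requires. Age at the visit is the natural choice because ulna length is measured at each visit, but the SAP should state it explicitly. Alternatively, state that heights already calculated under Protocol Table 4 are used without recalculation.

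Separately, check whether the HOPE-2 body-surface-area calculation cited in SAP 6.4 takes this derived height as input and, if so, confirm that the capped value is used.

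The cost is one line of SAP wording and one line of code for height and BMI, with no new data. The body-surface-area item is a check only; whether it leads to any change depends on a calculation these documents do not show.

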# 5.4 General Medical History

General medical history will be coded using Medical Dictionary for Regulatory Activities (MedDRA) version 23.1. General medical history data will include the new relevant and significant medical history between the completing the HOPE-2 trial and the start of the HOPE-2-OLE trial.

Medical history will be listed and summarized for the safety population. The summary will be presented by MedDRA System Organ Class (SOC) and Preferred Term (PT). At each level of subject summarization, subjects who experience more than 1 medical history PT within an SOC will be counted only once in the SOC.

# 5.5 DMD Medical History

The following DMD medical history will be listed and summarized for the safety population:

- Age at diagnosis (years),
- Age at first use of chronic glucocorticoids (years),
- Loss of stair climb and age at loss of stair climb (years),
- Loss of stair descend and age at loss of stair descend (years),
- Use of a walker and age at first walker use (years),
- Part-time use of a manual/power wheelchair or scooter and age at first part-time use of a manual/power wheelchair or scooter (years),
- Transition to full-time use of a manual/power wheelchair or scooter and age at first full-time use of a manual/power wheelchair or scooter (years),

- Start of non-invasive ventilatory support and age at non-invasive ventilatory support started (years),
- Use of a mechanical cough assist device and age at first mechanical cough assist device use (years),
- History of spine surgery,
- History of symptomatic heart failure and age at first symptoms of heart failure (years), and
- History of medical (non-surgical) hospitalizations.

# 5.6 Prior and Concomitant Medications

Prescription and over-the-counter medication use will be coded to drug class, preferred drug name, and generic/trade drug name using the World Health Organization Drug Global (WHODrug Global) dictionary, version September 2020. A full medical chart review will be conducted in order to reconcile cardiac and systemic steroid medications received by subjects either prior to or on the HOPE-2 study with records of prior cardiac and systemic steroid medications on the HOPE-2 OLE study.

Frequencies and percentages of subjects in the safety population who report or receive any prior and/or concomitant medications will be displayed and listed together by WHODrug Global Anatomic Therapeutic Chemical (ATC) Level 2 and preferred name. In addition, systemic cardiac medication (omitting supplements), systemic steroids, and pre-treatment (pre-infusion) steroids medications will be summarized and listed separately. Systemic cardiac medications will be tabulated and listed by therapeutic subgroup (i.e., ATC Level 2) and preferred name, while systemic and pre-treatment steroids will be tabulated and listed by preferred name.

At each level of subject summarization, subjects who report use of one or more medication within that level will be counted once for that level.

# 5.7 Planned Medical/Surgical Procedures

All reported elective medical and/or surgical procedures (e.g., wisdom tooth extraction) that are not the result of an AE will be displayed for the safety population in a subject listing. For each procedure, the type of procedure, indication, and start/end date will be reported.

Any administered medication(s) related to the planned medical/surgical procedure(s) will be captured as a concomitant medication(s).

# 5.8 IP Administration

Details of IP administration will be summarized and listed for the safety population. The number of subjects who complete the IP infusion at each visit will be summarized. This is defined as subjects who receive (without interruption or syringe pump interrupted and restarted) both IP syringe administrations. For each visit and each IP syringe administration, the total dose delivered (mL) from both the first and second IP syringes, the number of subjects who receive the contents of both IP syringes, the reasons administration of both IP syringes was not completed, duration of IP administration (minutes), and total dose of IP syringe delivered (mL)

will be summarized. In addition, for the second IP syringe, the reasons the second IP syringe was not administered will also be summarized.

# 5.9 Subject Study Progress

A listing of study progress by subject will show dates of per-protocol study visits and unscheduled visits. The number of subjects who complete each visit will be summarized.

# 5.10 Subject Disposition

All screen failures will be listed, along with the primary reason for screen failure, for the enrolled population.

Subject disposition will be summarized for the safety population. The number of subjects who complete the study, the number of subjects who discontinue from the study, and the primary reason for discontinuation will be summarized.

# 6 EFFICACY ANALYSES

Listings and summaries of the efficacy parameters will be prepared for the Safety population, unless indicated otherwise, and summarized as described below for each efficacy parameter. This is an open-label extension study with a specified hierarchical testing order; however, for descriptive purposes, p-values will be calculated for each outcome even if the step in the hierarchy is not met. There will be no adjustment for multiplicity of analyses.

### 6.1 PUL Scale

The PUL 2.0 was designed specifically for assessing upper limb function in ambulant and nonambulant DMD patients. All the tasks included in the PUL were selected to address patient-prioritized activities of daily living that are typical, regardless of age. The PUL includes an entry item to define the starting functional testing level for a subject. The remaining PUL items are divided into 3 regional dimensions: high-level (shoulder), mid-level (elbow), and distal level (wrist and hand). Trial subjects will complete testing for PUL 2.0 in the same preferred arm throughout the course of the trial.

All observed values will be listed. Observed totals and changes from baseline for each dimension [high-level (shoulder), mid-level (elbow), distal level (wrist and hand)] will also be listed.

# 6.2 Primary Efficacy Endpoint

The primary efficacy endpoint is the change from baseline (Day 1) to Month 12 in the PUL 2.0 Combined Total Score (high-level + mid-level + distal level dimensions). Observed and changefrom-baseline values will be summarized (n, mean, SD, minimum, and maximum). The 95% confidence intervals (CI) for the mean estimates also will be displayed.

To place the change from baseline (Day 1) for the PUL 2.0 Combined Total Score in context of the preceding HOPE-2 study and the Gap Phase, the following observed and change from baseline values, where not already tabulated, will be summarized (n, mean,

SD, minimum, and maximum) along with the 95% confidence intervals (CI) for the mean estimates. Figures will be provided for mean change for the four scenarios below.

- Non-treatment mean change HOPE-2 vs. Gap Phase: Change from the HOPE-2 baseline to Month 12 HOPE-2 [Main Phase] for the subjects in OLE study who were placebo subjects in HOPE-2 study and for these same subjects the change from Month 12 HOPE-2 to baseline (Day 1) HOPE-2-OLE [Gap Phase].
- On-treatment mean change HOPE-2 vs. HOPE-2-OLE:
  - Change from HOPE-2 baseline to Month 12 [Main Phase] for subjects in the OLE study who were deramiocel subjects in HOPE-2 study.
  - Change from HOPE-2-OLE baseline (Day 1) to Month 12 HOPE-2-OLE for subjects in the HOPE-2-OLE study who were on the placebo arm in HOPE-2 study.
- Gap Phase mean change comparison: Change from Month 12 HOPE-2 to baseline (Day 1) HOPE-2-OLE [Gap Phase] for the subjects in the HOPE-2-OLE study who were deramiocel subjects in the HOPE-2 study compared with the subjects in the HOPE-2-OLE study who were placebo subjects in the HOPE-2 study. As a reference, the change from HOPE-2 baseline to HOPE-2 Month 12 for subjects in the HOPE-2-OLE study who were deramiocel subjects in HOPE-2 study will be included.
- Year over year mean change during HOPE-2-OLE: For the safety population of the HOPE-2-OLE each year's change will be compared.
  - Change from HOPE-2-OLE baseline (Day 1) to Month 12 HOPE-2-OLE (Year 1).
  - Change from Month 12 HOPE-2-OLE to Month 24 HOPE-2-OLE (Year 2)
  - Change from Month 24 HOPE-2-OLE to Month 36 HOPE-2-OLE (Year 3)

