### Efficacy

Functional capacity assessed by PUL 2.0 will be performed at Day 1, Months 3, 6, 9, 12, 15, 18, 21, 24, 27, 30, 33, 36, 39, 42, 45, 48, 51, 54, 57, and 60.

Assessment of the Left Ventricular Ejection Fraction (i.e., cardiac MRI) will be assessed at the Month 24, Month 36, Month 48, and Month 60 visits.

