## 13.6. Efficacy Analysis

Efficacy will be evaluated at the 3, 6, 9,12, 15, 18, 21, 24, 27, 30, 33, 36, 39, 42, 45, 48, 51, 54, 57, and 60 month follow-up visits, with changes from baseline assessed for pre-specified endpoints.

Descriptive statistics will be used to summarize changes from baseline in the PUL 2.0 scores. Additional analyses will be conducted to assess the treatment effect and potential disease modification evidence, as outlined in the SAP.

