# 6.3 Secondary Efficacy Endpoints

The *secondary efficacy endpoints* include the change from baseline (PUL 2.0: HOPE-2-OLE Baseline, Cardiac MRI: HOPE-2 Month 12) through Month 60 for the following:

- Upper body functionality using PUL 2.0 assessment (i.e. Upper level PUL:2.0) at Months 12, 24, 36, 48, and 60
- Distal level PUL 2. at Month 12, 24, 36, 48, and 60
- Mid-level (elbow) PUL 2.0 at Month 12, 24, 36, 48, and 60
- LVEF (i.e. Cardiac MRI) at Month<del>,</del> 24, 36, 48, and 60.
- Left Ventricular End Systolic Volume, Indexed (Cardiac MRI) at Month, 24, 36, 48, and 60.
- Left Ventricular End Diastolic Volume, Indexed (Cardiac MRI) at Month, at Month 24, 36, 48, and 60.
- Other cardiac parameters, including but not limited to mass, unindexed volumes, and end diastolic and end systolic wall thickness at 24, 36, 48, and 60.

Observed values and change from baseline will be summarized (n, mean, SD, minimum, and maximum) for all secondary endpoints. Descriptive statistics for the External Comparators, ECP and ECC (section 6.4) will be presented for comparison with endpoints for which data are available.

Further comparisons will be formally made for the 24- and 36-month visits (if available) utilizing real-world evidence from external sources. The data and methods utilized for these comparisons is described in the next section.

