The treated and matched controls from the ECP/ECC will be compared using a continuous-time, random slope mixed model with age, baseline, and treatment-by-time interaction. If significant baseline imbalances persist after cohort matching, a baseline-by-treatment interaction term will be included in the model. Slope differences between groups will be presented along with the estimated treatment difference at 24 months (for ECC) and 36 months (for ECP) with corresponding 95% confidence intervals and associated two-sided p-values. The Kenward Roger approximation will be utilized to calculate denominator degrees of freedom. A percentile rank transformation will be applied to the change from baseline and baseline values in case model assumptions are violated.

Furthermore, a global statistical test (GST) may be employed to explore the totality of evidence across multiple cardiac endpoints, such as Left Ventricular Ejection Fraction, Indexed Left Ventricular End Systolic Volume, Indexed Left Ventricular End Diastolic Volume, and other cardiac MRI measures collected in HOPE-2 OLE and in the ECC. The GST will be constructed as follows:

• For each distinct parameter in the GST, calculate the standardized change from baseline as follows:

$$chg'_{i,t,p} = \frac{x_{i,t,p} - \mu_p}{\sigma^{pooled}_{t,p}}$$

where *i*, *t*, *p* represent the *i*th subject, the timepoint (visit) *t*, and the *p*th parameter in the GST, *x* represents the raw score (analysis value),  $\mu$  represents the mean baseline value for parameter,  $\sigma^{pooled}$  is the standard deviation of  $x_{t,p}$  pooled between control and treatment arms, and *chg'* is the standardized change from baseline.

Then, by subject and visit, calculate the mean standardized change from baseline as:

$$chg_{i,t}^{gst} = \frac{1}{n} \sum_{p=1}^{n} chg_{i,t,p}',$$

where  $chg^{gst}$  represents the change from baseline score of the GST.

Baseline values will be calculated in the same manner using baseline analysis values for each parameter and only with the baseline visit. If any of the baseline components do not have a calculable baseline value, baseline will be calculated from the available measures. Scales will be directionally aligned in determination of the final score.

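### The year-over-year PUL 2.0 comparison has no fixed subject set and no longitudinal model, so drop-out related to decline could look like slowing; separately, it stops at Year 3 of 5.

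*SAP*

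**What the plan says.** SAP 6.2 sets the change in the PUL 2.0 Combined Total beside HOPE-2 and the Gap Phase in four scenarios. The fourth is a year-over-year comparison: "For the safety population of the HOPE-2-OLE each year's change will be compared". Three changes are listed: Day 1 to Month 12, Month 12 to Month 24, and "Change from Month 24 HOPE-2-OLE to Month 36 HOPE-2-OLE (Year 3". The output is descriptive (n, mean, SD, minimum, maximum and a 95% CI for the mean), and "Figures will be provided for mean change for the four scenarios below".

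The data collected go much further. The protocol synopsis states that "Functional capacity assessed by PUL 2.0 will be performed at Day 1, Months 3, 6, 9, 12, 15, 18, 21, 24", and the list continues every three months to Month 60. Protocol 13.6 says "Efficacy will be evaluated at the 3, 6, 9,12, 15, 18, 21, 24, 27, 30", again continuing to Month 60.

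On missing scores, Protocol 13.5.2 allows only linear interpolation of PUL 2.0 items between visits where they were observed, and SAP 4.4 confines this to modelling. SAP 4.4 also leaves early-termination data that fall outside every visit window out of analyses and summary tables.

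For the later years, SAP 6.3 lists "Upper body functionality using PUL 2.0 assessment (i.e. Upper level PUL:2.0) at Months 12, 24, 36, 48, and 60", together with the distal and mid-level dimensions at the same months, and says "Observed values and change from baseline will be summarized (n, mean, SD, minimum, and maximum) for all secondary endpoints". The only longitudinal model is in SAP 6.4, for the external comparison, which gives the "estimated treatment difference at 24 months (for ECC) and 36 months (for ECP" and is run only if suitable controls can be found.

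**The concern.** Each annual mean needs a score at both ends of the year. Because nothing fills visits after drop-out, the Year 1, 2 and 3 means can rest on different subjects. This is an inference from the safety-population wording and the missing-data rules; the SAP does not say it outright. In a progressive disease, loss linked to progression is plausible. If it occurs, those remaining have milder rates on average, and the annual loss shrinks from year to year although no individual has slowed. A figure of mean change by year invites a reading of durable benefit, and with 13 subjects a few exits are enough to alter it.

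A second, separate gap is coverage. The extension runs 60 months, but the comparison ends at Month 36 and uses 4 of the 21 scheduled PUL 2.0 assessments.

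**Working it through.** The documents give no slope, SD, drop-out rate or power for this comparison, so there is no plan figure to reproduce. From the documents: 13 subjects (SAP 3.1 and 4.1) and quarterly visits (21 to Month 60, 13 to Month 36). Everything else below is assumed.

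**1. Loss of the fastest decliners.** Let each subject have a constant annual rate, normal with mean m and standard deviation SD, so true slowing is zero. If the fastest k of 13 leave, the expected mean of the rest is m + SD × d(k). By simulation d(1) = 0.14, d(2) = 0.26, d(3) = 0.37, d(4) = 0.48.

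- m = -2.0, SD 1.5, k = 3: -2.0 + 1.5 × 0.37 = -1.45, an apparent slowing of 0.55/2.0 = 28%.
- m = -2.0, SD 2.0, k = 3: -1.26 (37%).
- m = -1.5, SD 1.0, k = 3: -1.13 (25%).
- m = -3.0, SD 2.0, k = 3: -2.26 (25%).
- m = -2.0, SD 1.5, with k = 1, 2, 4: -1.79, -1.62, -1.29.
- Three subjects leaving at random: -2.00 stays -2.00.

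**2. Drop-out that depends on observed decline.** Rates of mean -2.0 and SD 1.5, residual SD 1.0, quarterly visits to Month 36. From Month 12 on, the log-odds of leaving after a visit are -4.2 + s × (-2.0 - observed annual rate since Day 1). The true change is -2.0 in every year. Annual means and same-subject differences come from 2,000 runs; the mixed model (random intercept and slope, year-specific slopes) was fitted in 150, with Monte Carlo error 0.04 to 0.05.

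| Dependence | Mean n at Month 36 | Planned means, Years 1, 2, 3 | Mixed model, Years 1, 2, 3 | Same subjects, Year 3 minus Year 1 |
|---|---|---|---|---|
| none (s = 0) | 11.6 | -2.01, -2.02, -2.00 | -1.98, -2.05, -1.95 | 0.01 |
| moderate (s = 0.8) | 10.4 | -2.02, -1.83, -1.70 | -1.99, -2.01, -2.00 | -0.11 |
| strong (s = 1.5) | 8.8 | -2.00, -1.62, -1.37 | -1.96, -2.10, -2.02 | -0.22 |

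The planned means drift towards zero only when drop-out depends on decline. The model stays near -2.0. The fixed set shows no false slowing but errs a little the other way: a subject with a favourable measurement error in Year 1 is more likely to be retained.

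**3. Precision gained from quarterly visits.** Let σ² be the measurement-error variance of one score. A two-visit change has variance 2.0σ². For a model linear within each year, the variances are the diagonal of (X'X)⁻¹σ² (fixed-effect part, independent residuals). The columns of X are an intercept and, for each year j = 1, 2, …, the time spent in that year, min(max(t - (j - 1), 0), 1), with t in years.

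- Data to Month 36: annual changes 1.28, 1.04, 1.28; cumulative 36-month change 1.18.
- Data to Month 60: annual changes between about 1.0 and 1.3; cumulative 60-month change 1.16.

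**The case against.** The comparison is contextual. SAP 6.2 offers it to put the primary result in perspective, the primary endpoint is at Month 12, and SAP 4.5 sets no test hypothesis. The n and 95% CI for each change are shown, SAP 5.10 summarises discontinuations with reasons, and Protocol 13.5.2 requires reasons for missing data and permits sensitivity analyses. This stands and keeps the point small. But n shows that subjects left, not whether they were declining faster. The missing-data sensitivity analyses are optional and unspecified, and those in SAP 6.5 concern LVEF.

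The later years and quarterly visits are not wholly ignored. Protocol 13.6 covers every quarterly visit, SAP 8 does not list dropping this as an exception, and SAP 6.1 lists all observed values. SAP 6.3 summarises the three dimensions at Months 48 and 60, and these add up to the Combined Total. That also largely stands. What is missing is a named Combined Total summary at those months with its own interval, which dimension-level SDs alone cannot supply, and the year-to-year changes.

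Four stronger readings are tempting, and the documents do not support them:

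- *That drop-out will create false slowing.* This needs drop-out related to decline, which the documents neither report nor exclude.
- *That stopping at Year 3 causes the bias.* It does not; if anything it leaves out the years with the most cumulative attrition.
- *That quarterly data cut the variance of the 36- and 60-month changes to 0.79σ² and 0.52σ².* Those follow from T²/Sxx for a single straight line (9/11.375 and 25/48.125). A single line assumes a constant rate and so cannot show slowing.
- *That the external comparison should be extended to Months 48 and 60.* The length of control follow-up is not given, so this cannot be judged here.

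**Conclusion.** The point holds as a weakness of a descriptive analysis. The year-over-year means have no fixed subject set and no longitudinal model, so decline-related drop-out could imitate slowing. Under the assumed rates, losing the fastest 3 of 13 gives an apparent slowing of about 25% to 37%; random loss gives none. The true size cannot be stated, because the documents give no rates, spread or drop-out. The coverage gap at Years 4 and 5 is real but separate, and the dimension scores in SAP 6.3 partly fill it. The primary endpoint at Month 12 is not affected. This is a cheap improvement, not a flaw that undermines the plan.

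**What to change.** In SAP 6.2:

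- Keep the observed annual means, with n for each year.
- Beside them, give the same means for the fixed set of subjects who have all the annual visits being compared, with n.
- Add the Year 4 (Month 36 to 48) and Year 5 (Month 48 to 60) changes in the Combined Total.
- Add a supportive mixed model on all quarterly Combined Total scores from Day 1 to Month 60, with random intercept and slope and year-specific slopes, reporting the annual changes for Years 1 to 5 with 95% CIs.

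The cost is SAP wording and one model on data already scheduled for collection. The model relies on scores being missing at random given those observed, and with 13 subjects its intervals will be wide. The fixed-set table can err slightly in the opposite direction, so the two should be read together. Neither removes floor effects: a subject near the bottom of the scale has little left to lose, and that too can look like slowing.
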